### Determination of Subjects for Analysis

All subjects that have follow-up visits after elevated night pacing was programmed OFF. This will include subjects completed 12 weeks of follow-up and subjects that had elevated night pacing programmed OFF at 4 weeks and completed 8 weeks of follow-up.

#### 7.9.9. Additional Exploratory Analyses

As this is a feasibility study with a relatively small sample size and no correction for multiple comparison, the ancillary objectives stated above were limited to the most likely possible outcomes predicted by the high rate pacing under investigation. There are many other potential exploratory analyses that could be of interest and could be performed. Foremost, although not explicitly stated in the protocol, it is possible that there might be no effect of the therapy at the 4 week follow-up visit, but that there is an effect of the therapy at the 8 week visit – particularly for those subjects with high rate pacing kept programmed to ON at the 4 week follow-up visit. Particularly for, but not limited to, any measurement that was trending towards significance at week 4, it will be of interest to test the 8 week measurement against the baseline measurement for significance of the change from baseline. If done, these tests should be performed analogously to the 4 week tests described within this section.

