**Figure 3: 95% Confidence Interval Widths for Various Proportions of 4 Week Safety and Tolerability Endpoint**

This section presents statistical considerations for the study design and provides a high-level description of planned analysis and reporting. More details will be given in a separate Statistical Analysis Plan (SAP) that will be completed before data freeze and unblinding for the primary objective analysis. Any deviation to the pre-specified statistical analyses will be noted in the study report.

As part of the exploratory/ancillary safety, tolerability and efficacy effects described in 10.20. Assessment of Efficacy, it will be of interest to characterize changes in collected measurements from baseline to 4 weeks, compare changes in collected measurements at 4 weeks to 8 weeks in the subjects randomized to the elevated night pacing ON arm to subjects randomized to the elevated night pacing OFF arm and compare changes in collected measurements at 12 weeks to Baseline, 4 and 8 weeks to see whether any therapeutic improvements are sustained after the therapy is discontinued.

The 4 week endpoints will characterize the magnitude of change as a result of the therapy. For MNLWHF and the 6 Minute Walk Test, positive changes could be due to placebo-related effects, since this phase of the study is single arm and unblinded. Efficacy changes from the 4 week to the 8 week visit in the ON arm versus the OFF arm would be indicative of actual therapeutic effects of elevated night pacing, as blinding would help mitigate any placebo effect. Safety and tolerability changes from the 4 week to the 8 week visit in the ON arm versus the OFF arm would be indicative of long term safety and tolerability of elevated night pacing for subjects for which the first 4 weeks of therapy were safe and tolerable.

If there are changes in any of the efficacy measurements from baseline to week 4 and/or improvements in any of the efficacy measurements in the ON arm compared to the OFF arm from week 4 to week 8, there may be additional analyses on the extracellular matrix biomarkers to correlate to the efficacy improvements.

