## 5. Investigation Plan

### 5.1. Study Design

The REVAMP Clinical Study will be a multi-center, prospective, randomized, single-blinded, clinical feasibility study. Subjects will be randomized in a 2:1 ratio to elevated night pacing ON or elevated night pacing OFF.

It is expected that up to 50 subjects may be enrolled to ensure 30 subjects undergo elevated night pacing at approximately 10 sites in the United States to ensure enrollment completion within the pre-specified timeframe.

[figure not shown]
The REVAMP study will be conducted as a Non-Significant Risk (NSR) IDE study. The REVAMP Research System does not include an investigational device; the ability to program a lower rate of 100 bpm is available in market-released pacemakers, and the Sleep function (which allows a different rate to be programmed for part of a 24-hour clock) is an approved feature in market-released pacemakers that will be used in the clinical study. The study will be conducted in compliance with 21 CFR Parts 11, 50, 56, 812.2(b)(1). This study does not require an IDE submission to FDA.

The Sleep Function will be programmed so that the pacemaker can deliver an elevated pacing rate of 100 bpm during the night for 5 hours and lower the rate during the daytime hours. This is within the FDA-approved programmable parameters of the Sleep Function feature.

The study will collect the following information: demographics, medical history, medications, standard physical, NYHA class, blood samples to measure NT-proBNP, Troponin and other biomarkers, echo

measurements, MN Living with Heart Failure Questionnaire, EQ-5D-5L Questionnaire, 6 Minute Walk Test, implanted device information, device interrogations, save-to-media, adverse events (including death), system modifications, and exit information. The MN Living with Heart Failure Questionnaire was chosen to measure the quality of life for subjects with heart failure, which includes a question on how well the subject is sleeping at night.

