### Analysis Methods

A paired comparison of the value at the end of the period compared to the value at the start of the period will be calculated. A one-sided paired t-test will be performed testing the hypothesis

$$H_0: \mu \leq 0$$

$$H_a: \mu > 0$$

Where  $\mu$  = difference in 6 Minute Walk Test distance from baseline to week 4 visit

SAS code similar to the following will be used to evaluate the 4 week 6 Minute Walk Test endpoint:

```
PROC TTEST;
  PAIRED sixminwalk0*sixminwalk4;
RUN;
```

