### Determination of Subjects for Analysis

All subjects that completed 4 weeks of elevated night pacing. Subjects that were unable to tolerate or withdrew from the treatment during the first 4 weeks because of safety or other issues will not be included in this efficacy analysis. Subjects that did not take the 6 Minute Walk Test at either baseline or week 4 will be assigned a distance of 0 for the missed visit. A sensitivity analysis may be done excluding subjects instead of assigning a distance of 0.

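### SAP 7.9.9's optional search for a week 8 therapy effect uses before-and-after tests with no concurrent control, so change shared by both arms can be read as an effect of pacing

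*SAP*

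**What the plan says.** SAP 7.9.9 lists further analyses that could be done. It puts first the possibility of no effect at week 4 but an effect of the therapy at week 8, "particularly for those subjects with high rate pacing kept programmed to ON at the 4 week follow-up visit". For this it says that "it will be of interest to test the 8 week measurement against the baseline measurement for significance of the change from baseline", with emphasis on measures trending at week 4 but without confining the test to them. On the form of the test: "If done, these tests should be performed analogously to the 4 week tests described within this section".

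The 4 week tests are before-and-after tests. For the 6 Minute Walk Test (SAP 7.9.5), "A one-sided paired t-test will be performed testing the hypothesis" that the mean change from baseline is not positive; MNLWHF (7.9.4) has the same form. Safety markers, continuous echo measures and biomarkers (7.9.2, 7.9.6, 7.9.7) use the two-sided version. Activity and binary echo measures use models with period or time only. None contains treatment arm. The 4 week analysis set opens with "All subjects that completed 4 weeks of elevated night pacing".

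A control group does exist from week 4. SAP 5.1 states: "Subjects will be randomized in a 2:1 ratio to elevated night pacing ON or elevated night pacing OFF". On size it states: "It is expected that up to 50 subjects may be enrolled to ensure 30 subjects undergo elevated night pacing".

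Protocol section 14 says of MNLWHF and the 6 Minute Walk Test over the first 4 weeks that "positive changes could be due to placebo-related effects, since this phase of the study is single arm and unblinded". It treats ON-versus-OFF differences from week 4 to week 8 as the evidence that would point to a real therapeutic effect.

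**The concern.** The question in 7.9.9 is causal: does pacing have an effect that appears only by week 8? The test offered answers a different one: has the mean moved since baseline? The interval from baseline to week 8 includes the whole single-arm, unblinded phase about which the protocol itself warns. A significant result would be compatible with pacing, placebo response, practice on the walk test, regression to the mean, or any mixture.

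The scenario in 7.9.9 is also the one where the OFF arm is most useful. If nothing has happened by week 4, the arms should part only after randomisation, and ON versus OFF addresses that directly.

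Giving priority to measures that trended at week 4 adds a smaller problem. The week 4 and week 8 changes share the same baseline value, so a baseline that is poor by chance both draws attention to a measure and flatters its week 8 result. SAP 7.5 plans no multiplicity adjustment, and 7.8 allows presentations while the study is running, so such a result could be reported as a late effect.

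**Working it through.** **Inputs.** From the documents: 30 paced subjects and 2:1 allocation, so 30 × 2/3 = 20 ON and 30 × 1/3 = 10 OFF if all reach week 4. Assumed: a test level of 0.05, because no level is stated for the paired tests, and a shared change c in units of the SD of the change score, because the documents give neither a placebo change nor an SD. Neither document gives a figure for 7.9.9, so there is none to reproduce.

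**Step 1: the paired test when pacing does nothing.** If every subject changes by c on average in both arms, the paired t statistic in n subjects is noncentral t with n − 1 degrees of freedom and noncentrality c√n. The one-sided rejection probability is P(T > t(0.95, n − 1)). For n = 20 the critical value is 1.729, and the noncentrality is 0.894, 1.342 and 2.236 for c = 0.2, 0.3 and 0.5.

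| Shared change (SD) | ON only, n = 20, one-sided | ON only, n = 20, two-sided | ON only, n = 16, one-sided | Both arms pooled, n = 30, one-sided | ON v OFF, 20:10, one-sided |
|---|---|---|---|---|---|
| 0 | 5% | 5% | 5% | 5% | 5% |
| 0.2 | 22% | 14% | 19% | 28% | 5% |
| 0.3 | 36% | 25% | 31% | 48% | 5% |
| 0.5 | 70% | 57% | 60% | 85% | 5% |

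The last column is simulated (50,000 trials per row) and ranges from 4.8% to 5.1%. The shared change cancels in the difference between arms. Pooling the arms makes matters worse, because OFF subjects then add sample size without acting as a comparator.

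**Step 2: emphasis on trending measures.** Let D4 and D8 be the changes from baseline to weeks 4 and 8. With equal variances σ² and a common correlation ρ between visits, Var(D4) = Var(D8) = 2σ²(1 − ρ) and Cov(D4, D8) = σ²(1 − ρ), so their correlation is 0.5 for any ρ. With no change at all, and selection on a one-sided week 4 p-value between 0.05 and 0.20 (an assumed window), the week 8 test in ON subjects rejects in 10% of simulated trials. With a window of 0.05 to 0.15 it is 11%.

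The randomised contrast escapes this. Write κ = Cov(D4, D8). The covariance of the ON mean of D8 with the pooled mean of D4 is (20/30)(κ/20) = κ/30. For the OFF mean it is (10/30)(κ/10) = κ/30. The difference is zero, and simulated ON v OFF false positives after selection are 4.9% (baseline to week 8) and 5.1% (week 4 to 8).

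**Step 3: what the randomised contrast costs.** For a true difference d its noncentrality is d/√(1/20 + 1/10) = d/0.387 on 28 degrees of freedom. One-sided power is 35%, 64% and 81% for d = 0.5, 0.8 and 1.0 SD. The paired test shows 70% at 0.5 SD, but that is the same 70% as in the Step 1 table: it detects change from any cause.

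**The case against.** The best defence is that the SAP already contains the right test and 7.9.9 is only an optional extra. Week 4 to 8 change is compared by arm for the safety markers, MNLWHF, walk distance, activity, echo and, conditionally, biomarkers (7.9.2 and 7.9.4 to 7.9.7). EQ-5D-5L also has a by-arm baseline to week 8 test. All of this stands and limits the harm.

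A reader might infer several stronger things that the documents do not support:

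- **That an ON-only test is required.** The section is conditional throughout and defines no analysis set. Its remark about ON subjects says where an effect may appear. Pooling would not supply a control, however.
- **That only trending measures are tested.** The SAP says the opposite. The 10% to 11% in Step 2 describes an emphasis under an assumed window.
- **That the protocol disowns all uncontrolled change.** Its placebo warning names MNLWHF and the 6 Minute Walk Test. Echo is read by a core laboratory blinded to arm and visit (Protocol 13.1), so placebo response is a weaker explanation there. The same section also says the 4 week endpoints will characterise change resulting from the therapy.
- **That a 7.9.9 result could overrule a null randomised one.** Nothing gives it that standing. The only stated aid to a decision is 4 week safety and tolerability (SAP section 6).

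It is also fair that OFF is not a perfect control. OFF subjects had 4 weeks of pacing, and Protocol 7.2 doubts that blinding will fully hold. Both limit the contrast, but neither gives the before-and-after test a control.

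**Conclusion.** The point holds as a modest, inexpensive improvement. The week 8 test in SAP 7.9.9 cannot separate a late effect of pacing from change common to both arms, and calling the analysis exploratory does not alter that. It is the wrong instrument for the question the section asks, and the trial has a better one. The concern is strongest for MNLWHF and the 6 Minute Walk Test.

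The size depends on an unknown shared change. At 0.2 to 0.5 SD the false-positive rate in 20 ON subjects is 22% to 70% one-sided or 14% to 57% two-sided, against about 5% for ON versus OFF. With no shared change and no selection it is the nominal 5%. These figures assume normal change scores, a 0.05 level and all 30 paced subjects reaching week 4. The selection figures also assume equal variances and equal correlation between visits. That ON versus OFF guards against placebo response assumes subjects stay blinded after week 4.

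**What to change.** Replace the closing two sentences of SAP 7.9.9 with wording to this effect:

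> A late effect will be judged by the randomised ON versus OFF comparison, for all measurements whatever their week 4 p-value. This will be the planned week 4 to 8 contrast or the baseline to week 8 change by arm, using ANCOVA on the baseline and week 4 values. Week 8 versus baseline changes within each arm will be described with confidence intervals and will not by themselves be taken as evidence of a therapy effect.

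Once baseline and week 4 are both covariates, the two outcomes give the same treatment coefficient, since they differ only by a linear combination of the covariates. The choice between them is then presentational, and the change is a small extension of the ANCOVA already allowed in 7.9.2.

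If the EQ-5D-5L analysis in 7.9.4 is used as a template, take its test form only. Its analysis set is limited to subjects who completed 8 weeks of pacing, which read literally leaves no OFF subjects.

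The cost is a few sentences and lines of code, with no new data. Precision falls to that of about 20 against 10 subjects. The contrast estimates continuing against stopping pacing at week 4, so a delayed effect of the first 4 weeks in OFF subjects would dilute it. The SAP should say so.

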## 7.10. Changes to Planned Analysis

There were a number of minor errors in the Statistical Design and Methods section of Version 3.0 of the REVAMP CIP. These errors include formatting issues, incomplete information and incorrect references. None of these issues require a change in the planned analysis specified in the CIP. These issues have been corrected in the SAP. The issues that have been identified include

- There is a reference to the MNLWHF score in the 8 week 6 Minute Walk Test Distance endpoint in the Analysis Methods section. The measured outcome should be distance rather than MNLWHF score.

In the event that the CIP is revised, the errors specified in this section should be updated in that revision.

## 8. Validation Requirements

All safety objectives will be validated at least at level II validation (peer review). Efficacy objectives will be validated at least at level III validation (self-validation). Any results used for abstracts or presentations may be validated at a more rigorous level.

